
Our study's specific aims are to:

- 1a: Develop the *PlaySmart* game through focus groups with up to 40 16-19-year old high school students, focus groups with up to 20 18-25-year-old young adults, interviews with up to 20 16-25-year olds, interviews with up to 20 opioid use disorder treatment providers and focus groups with up to 20 stakeholders (educators, prevention specialists, etc.).
- 1b: Pilot-test *PlaySmart* with 30 adolescents, using methods from our prior research ^{13,16,19,20,33}
- 1c: Develop implementation strategies and partners through focus groups with 50 School Based Health Alliance affiliates and 30 adolescents from the Youth Advisory Council.

4. **Research Plan:** Summarize the study design and research procedures using non-technical language that can be readily understood by someone outside the discipline. **Be sure to distinguish between standard of care vs. research procedures when applicable and include any flowcharts of visits specifying their individual times and lengths.** Describe the setting in which the research will take place.

This protocol will be conducted over two years. The outline below highlights the research plan. We will conduct focus groups and interviews to help inform the development of a digital intervention and then evaluate the feasibility, acceptability, and usability in a pilot study. Eight focus groups with five adolescents (n=40), aged 16-19, will be conducted locally over the course of six months. Each group will meet once for approximately 1-1.5 hours after school in a classroom. When the study is introduced to parents/guardians and students, we have always stressed that a stipulation of our studies requires reliable transportation to/from our studies. In certain cases where transportation is not available, we will provide a bus pass.

In addition, we will conduct 4 focus groups with approximately five 18-25-year-old young adults (n=20). Each focus group will meet once for approximately 1-1.5 hours at a private location on a college campus, a public meeting space such as a library, or in a location at Yale Medical School. All participants will provide consent. Our goal is to learn about the perceptions and experiences of opioid misuse among young adults to inform our intervention.

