The entire pilot study phase for this project will be completed over the course of six months. We plan to enroll 30 adolescents, aged 16-19 to playtest our game. We will meet with participants between 2-4 times for approximately 1-1.5 hours each time, over the course of two to four weeks. Participants will complete baseline measures, two gameplay sessions and a post-assessment to measure feasibility, acceptability, and usability. Each participant will complete the pilot study within two to four weeks. We will meet with them after school in a classroom (securing room with coordination from our school partners). When the study is introduced to parents/guardians and students, we have always stressed that a stipulation of our studies requires reliable transportation to/from our studies. In certain cases, we will provide a bus pass.

All participants will be assigned a study identification number to link pre/post assessments and to conduct focus groups. Data collection and storage will be conducted according to standardized protocols. The link between participant's identity and the study number is confidential and will be kept separate from all study data. Research data, such as informed consents/assents, transcriptions, and field notes, is kept in cabinets that are locked except when in use, and access to

data stored in computers is password protected. We will collect participants' names, school, gender, grade level, age, race, and ethnicity. Names will not be sent to any third parties. Any data shared with NIH or other third-party organizations will be aggregate data. We will collect this information and it will be stored in a secured database.

The Yale University Human Subjects Committee (the committee that reviews, approves, and monitors research on human subjects) may inspect study records. All published results will be group data. Information that will be collected during the focus group interviews will be erased 12 months after the completion of the study and after review of their content has been completed.

1. Formative and development work: (1 year)

- a.) We will work iteratively with our target audience of 16-19-year old adolescents within schools to develop videogame content, collecting qualitative data for the videogame intervention and refining our logic model with input from 8 focus groups of 5 adolescents each (n=40), aged 16-19 and 4 focus groups of 5 young adults aged 18-25 (n=20).

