- a.) We will work iteratively to develop videogame content, conducting 8 focus groups of 5 adolescents each (n=40), aged 16-19 and 4 focus groups of 5 young adults each (n=20), aged 18-25 collecting qualitative data for the videogame intervention and to refine our logic model.
- b.) Working with our community school partners, we will engage 1-2 schools and school-

based health centers to **recruit** 30 adolescents for our subsequent pilot study. Given participants are only involved in the pilot study for several weeks and given our track record of having retained the majority of participants for over two years of a prior RCT, we are not concerned about retention.

- c.) We will **pilot-test** the intervention with 30 adolescents, aged 16-19, in conjunction with their schools, to evaluate the **acceptability** of the game. To garner feedback, we will collect data (both qualitative and quantitative) after the completion of game play sessions. The pilot will either be conducted virtually or in person. For the in person segment of the pilot, all COVID-19 protocols and procedures that are in place at our partner school site will be followed.
- d.) We will also **pilot procedures** such as assuring the gameplay sessions go smoothly and that data collection is streamlined in anticipation of conducting the subsequent RCT.
- e.) We will develop a game implementation manual that will be used during the subsequent RCT, as needed, by school and school-based health center staff.
- f.) As part of our focus groups with school-based health affiliates, we will collect focus group data for our formative and development of a videogame intervention from the Youth Advisory Council (n=15) and School-based health affiliates (n=25) at the annual School-Based Health Alliance Convention. This includes data on implementation strategies such as barriers and facilitators and to share perceptions of the newly created game and provide input on the game implementation manual. This will take place at the annual School-Based Health Alliance Convention with our national partners who will help recruit participants for the Youth Advisory Council and School-Based Health Alliance.

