The subject population for this project is adolescents between the ages of 16-19. Young adults aged 18-25 will be recruited for focus groups as well. There are also adults (19-80) that will be recruited to participate in separate focus groups at the Convention.

For this study, 8 focus groups of 5 adolescents each (n = 40), boys and girls in Connecticut, aged 16-19 will participate in the focus groups and 30 adolescents, boys and girls, aged 16-19 will participate in the pilot testing of the adapted game (2 groups of 3 adolescents will participate virtually and 6 groups of 4 adolescents each will participate in person at their school site while following COVID-19 guidelines). These adolescents will be recruited from the high schools that we already have established partnerships with, such as Maloney High and Hamden High. In addition, we will conduct 4 focus groups of young adults aged 18-25 (N=20) in Connecticut. These young adults will be recruited from local universities. Additionally, 30 youth (16-19) over the course of two years (e.g., meeting annually) from the national School-Based Health Alliance (SBHA) National Convention will also be recruited to participate in focus groups for the project.

For the focus groups with the adults, 50 adults (19-80) who are affiliates of the SBHA will be recruited over the course of two years (e.g., meeting annually) during the national SBHA Convention to participate in the project and will receive information sheets. Their role represents various positions within school-based health centers across the nation. Their role in this study is to be part of our focus groups to help inform game development and implementation strategies.

For the individual interviews, up to 20 participants aged 16-25 who are currently receiving treatment for opioid use disorder will be recruited to participate in this study. The Director of Research at the APT Foundation has approved and will post flyers (see example of the flyer attached) on site at the APT Foundation. Other interview participants may be recruited through provider referral. Interested participants will contact our research team to participate.

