For interviews with treatment providers of opioid use disorder, up to 20 adults (19-80) who have treated individuals aged 16-35 for opioid use disorder within the last 5 years will be recruited. Clinical directors at each APT Foundation location will inform treatment providers about our study and other colleagues may be contacted via email and from snowball sampling from other providers that participate in the interviews. Interested participants will contact our research team to participate.

For focus groups with stakeholders (educators, prevention specialists, etc.), approximately 20 adults (19-80) will be recruited. Our team may collaborate with various organizations (e.g., FCD Prevention Works, First Book) to recruit participants. Interested participants will contact our research team to participate.

Subject classification: Check off all classifications of subjects that will be specifically recruited for enrollment in the research project. Will subjects who may require additional safeguards or other considerations been enrolled in the study? If so, identify the population of subjects requiring special safeguards and provide a justification for their involvement.

181 Children	181 Healthy	 Fetal material, placenta, or dead fetus
 Non-English Speaking	 Prisoners	 Economically disadvantaged persons
 Decisionally Impaired	 Employees	 Pregnant women and/or fetuses
 Yale Students	 Females of childbearing potential	

NOTE: Is this research proposal designed to enroll children who are wards of the state as potential subjects?

Yes **No**

7. Inclusion/Exclusion Criteria: What are the criteria used to determine subject inclusion or exclusion?

Adolescent participants must: 1) attend high school that has a school-based health center, and 2) be 16-19 years (grades 9-12) to participate in the game development focus groups or pilot testing OR they must be a member of the School-Based Health Association Youth Advisory Council to solely participate in the focus groups.

Young adult game development focus group participants must be 18-25 years old.

Adult participants that will be participating in focus groups during the game development phase must be national school-based health center personnel and be between the ages of 19-80.

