Interviews with individuals in treatment: Participants must be between the ages of 16-25, receiving treatment for an opioid use disorder, a device to access the internet for the virtual interview and be able to sit for 60-90 minutes in an interview.

Treatment providers: Participants must be adults between the ages of 19-80, have provided medical treatment for individuals aged 16-35 in the last 5 years for opioid use disorder, a device to access to the internet for the virtual interview, and be able to sit for 60-90 minutes for an interview.

Stakeholders: Participants must be between the ages of 19-80, qualify as a stakeholder in the project (e.g., an educator, prevention specialist, etc.), have access to a device to access the internet for a virtual focus group, and be able to sit for 60-90 minute for a focus group.

8. How will eligibility be determined, and by whom? Write here

For youth focus groups & pilot study: In order to be eligible for either the youth focus groups or the pilot study, adolescent participants must: 1) attend a high school that has a school-based health center, 2) be 16-19 years (grades 9-12), and 3) coordinate reliable transportation home or to their next location. The research assistant (in collaboration with the designated school liaison/champion) will screen for eligibility and discuss the study with the participant and their parent/guardian.

For young adult focus group participants: In order to be eligible for the young adult focus group the participant must be between the ages of 18-25.

For adult focus groups: In order to be eligible for the adult focus group, the participant must be a school-based health center affiliate and between the ages of 19-80.

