- a. Targeted for enrollment at Yale for this protocol: 150
- b. If this is a multi-site study, give the total number of subjects targeted across all sites: *Write here*

2. Indicate recruitment methods below. Attach copies of any recruitment materials that will be used.

181 Flyers	 InterneUwebpostings	D Radio
181 Posters	 Massemail solicitation	 Telephone
 Letter	 Departmental/Center website	D Television
 Medical record review*	D Departmental/Center research boards	D Newspaper
 Departmental/Center newsletters	D Web-based clinical trial registries	D Clinicaltrials.gov
 YCCI Recruitment database	 Social Media(Twitter/Facebook):	

181 Other: Meeting with school and program staff, school orientations and open houses, announcements in schools, also SBHA representative send emails to affiliates and YAC for the Convention

* Requests for medical records should be made through JDAT as described at <http://medicine.yale.edu/ycci/oncore/availableservices/datarequests/datarequests.aspx>

3. Recruitment Procedures:

- a. Describe how potential subjects will be identified. *Write here*
- b. Describe how potential subjects are contacted. *Write here*

Who is recruiting potential subjects? *Write here*

For game development focus groups, students will be recruited through flyers and announcements to the student general population via school meetings and physical education/health classes. Members of our team will also make lunchroom and classroom announcements about our project. We will also ask school teachers/administrators to share announcements about our study to their students. Potentially interested students will receive an information sheet describing the purpose of the research activity and they will be able to agree or decline.

For the young adult focus groups, participants will be recruited through flyers and announcements. Interested participants will be encouraged to contact our team through a number on the flyer. We will work with local universities to follow their protocols in recruiting participants from their school.

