For interviews conducted with participants aged 16-25 who are currently in treatment, we will post flyers at the APT Foundation where participants are able to contact a member of our research team if s/he is interested in participating in our research study. We will work with the APT Foundation to follow their strict research protocols in recruiting participants from the APT Foundation. In addition, providers can refer individuals that might be interested in participating in the interview;

For interviews with treatment providers, a member from our team will contact the clinical director of each APT site. The clinical director will then inform providers of the opportunity. Interested participants will contact a member of our team. We will work with the APT Foundation to follow their strict research protocols in recruiting participants from the APT Foundation. In addition, we will recruit via email and from snowball sampling from other providers that participate in the interviews to recruit those treatment providers that may not be associated with the APT Foundation.

For stakeholder focus groups, our team will work with organizations such as FCD Prevention Works and First Book to recruit participants for our study. Organization leaders will share information about the focus group opportunity to their contacts. Interested participants will contact a member of our team.

Recruitment/enrollment and conduct of this pilot study will be in collaboration with the school-based health center at one Connecticut high school where there is a high prevalence of high-risk adolescents and where we already have developed a partnership. The recruitment plan will replicate similar plans conducted in the last 10 years at our lab around sensitive data. They include recruitment via flyers and announcements at the school. As we have done with other studies, examples include providing announcements to teachers/staff to share in classrooms, introductions during classes, and providing information about the study to all interested students during lunch. Flyers and information will highlight this is a research study developing and evaluating a digital intervention for substance use prevention and to help adolescents make better healthier decisions.

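### Should students who helped shape the game in a school focus group be barred from the 30-person pilot, or flagged in it?

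*Combined protocol and SAP*

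**What the plan says.** Section I.7 sets the adolescent criteria once for both activities: attendance at a high school with a school-based health center, and to "be 16-19 years (grades 9-12) to participate in the game development focus groups or pilot testing". Youth Advisory Council members come in by a separate route that limits them to focus groups. School students have no matching limit.

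Section I.8 opens its screening list with "In order to be eligible for either the youth focus groups or the pilot study, adolescent participants must: 1) attend a high school" and goes on to age, grade and transport. Prior participation is not on the list.

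Section I.6 describes the 40 focus-group students and the 30 pilot students together and says "These adolescents will be recruited from the high schools that we already have established partnerships with". Under Section III.3, for the focus groups, "students will be recruited through flyers and announcements to the student general population via school meetings and physical education/health classes". Of the pilot recruitment methods the same section says "They include recruitment via flyers and announcements at the school", and it places the pilot at one Connecticut high school. Section I.4, item 2b, says one to two schools.

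On exposure, Section I.4 says of the school focus groups: "Each group will meet once for approximately 1-1.5 hours after school in a classroom". The pilot has baseline measures, gameplay sessions and "a post-assessment to measure feasibility, acceptability, and usability".

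**The concern.** The focus groups supply content for the game, and the pilot then asks students what they think of the game. A student who did both is not a fully independent judge. Such a student might be kinder to a product they helped make, or harsher if their ideas were not used. Earlier discussion of opioid misuse with the study team might also colour their baseline answers.

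The two samples share eligibility rules, partner schools and similar recruitment channels, and both are paid. Overlap is therefore possible. With only 30 pilot students, each returning student carries 1/30 = 3.3% of the sample. If nobody counted them, a reader of the pilot report would not know how many of the 30 had contributed content.

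**Working it through.** **Counts in the plan.** Section I.6 gives the pilot as 2 groups of 3 plus 6 groups of 4: 2 × 3 + 6 × 4 = 30, as stated. The school focus groups are 8 × 5 = 40, as stated. Taken literally, the rules allow an overlap of 0 to min(40, 30) = 30 students.

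**How likely overlap is.** The upper bound of 30 is logical, not realistic. A returning student must have been in a focus group, still be in grades 9-12 at the pilot, attend one of the one or two pilot schools, and volunteer again.

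- Timing: the Section I.2 table marks focus groups in Year 1 only and pilot testing in Year 2 only. Section I.4, item 1a, lists the same 8 groups in the formative year. Item 2a, under the pilot-year heading, again speaks of "conducting 8 focus groups of 5 adolescents each (n=40), aged 16-19". This reads as a repeat of item 1a, because item 2b then calls the pilot subsequent.
- Expected number: let F be the focus-group students still enrolled at the pilot school(s), and M the eligible students there. If the 30 were a random draw, the expected overlap would be 30 × F/M. The documents give neither figure, so these values are assumptions:

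| M | F = 20 | F = 40 |
|---|---|---|
| 300 | 2.0 | 4.0 |
| 600 | 1.0 | 2.0 |
| 1,200 | 0.5 | 1.0 |

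F = 40 is the extreme case in which every focus-group student attends a pilot school and is still enrolled. Students who volunteer once may be more likely to volunteer again, so the true number could be above the random-draw figure.

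**What overlap would do.** Let k be the number of returning students and d the difference in their proportion rating the game acceptable. The overall proportion shifts by (k/30) × d. The documents give no value or sign for d. For assumed sizes of 0.10 to 0.30:

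| k | Shift in percentage points, either direction |
|---|---|
| 3 | 1.0 to 3.0 |
| 6 | 2.0 to 6.0 |
| 10 | 3.3 to 10.0 |

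The row k = 10 is 10/4.0 = 2.5 times the largest random-draw figure above.

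**Against sampling error.** At an assumed acceptability of 80%, the 95% Wilson interval with n = 30 is 0.627 to 0.905, a half-width of (0.905 − 0.627)/2 = 0.139, or about 14 points. Every shift in the table is smaller. Leaving out 6 returning students (n = 24) gives 0.604 to 0.913, so a with-and-without comparison would show little.

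**Whether overlap can be found later.** Section I.4 gives every participant a study number and collects names and schools. Section IV keeps a master file of names with study numbers. Section III.3 has the study team carry out recruitment. The erasure dates in Section I.4 for focus-group material (12 months in one place, 24 months for recordings in another) both fall after the study ends, so neither removes the means of checking during the pilot.

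**What the rating feeds.** Section I.4, items 2d and 2e, link the pilot to the later RCT through session procedures, data collection and an implementation manual. The documents state no acceptability threshold and no go/no-go rule, and Section I.4 describes no comparison arm for the pilot.

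**The case for a change.** The best case for a change is that it costs almost nothing. One eligibility sentence or one yes/no screening item, checked against a file already planned, would settle the matter. The target would stay at 30 and the recruitment pool would shrink by at most 40. The limit on Youth Advisory Council members shows that the authors could restrict participation where they wished. Section V also speaks of replicating the intervention if the pilot shows it to be effective, so the pilot results may be read as more than a playtest.

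Part of this stands. No rule separates the samples, and no check is scheduled. The enrollment target of 150 in Section III.1 equals 40 + 30 + 30 + 50, which suggests that the two adolescent samples were counted as different people. This is weak support, because the document does not show that sum, and adding the young adults, interviewees, providers and stakeholders (4 × 20 = 80) would give 230.

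The rest does not carry the point. Focus-group students have not played the game on the plan's description, so they too are new to it when the pilot begins. One discussion of 1 to 1.5 hours gives little reason to expect different usability ratings. In an openly iterative development project, letting a contributor return and judge the result is a legitimate choice. The Section V remark sets no criterion that overlap could tip.

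**Conclusion.** No change to the plan is needed. Sections I.7 and I.8 are silent on whether a focus-group student may join the pilot. The study team can fill that gap by consulting its own records and giving the number of returning students in the pilot report. Excluding them is a design preference on which reasonable statisticians would differ.

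The likely size is small. Overlap of about 0.5 to 4 students is expected under random recruitment with the assumed school sizes, and up to 4 returning students move the overall rate by at most (4/30) × 30 = 4 points at the largest assumed difference. The 95% interval extends about 14 points either side. These figures rest on assumed values for school enrollment, rating difference and acceptability level, and the direction of any shift is unknown.

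The conclusion also rests on the Section I.2 timeline being followed, on the master file covering both activities, and on the pilot rating not being tied to a pass mark. If a pass mark were set, or the pilot were offered as evidence of effect, the number of returning students would deserve a planned count.
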